7.11.5 Vital Signs

Vital signs are to be recorded for all patients and will include pulse, blood pressure, respiration rate, oxygen saturation, and temperature.

7.11.6 Electrocardiogram

An electrocardiogram (ECG, 12-lead) will be performed in accordance with the clinical site’s standard practice(s). Electrocardiogram recordings will be read locally at the clinical site by a qualified cardiologist. The ECG will include assessment of heart rate, sinus rhythm, atrial or ventricular hypertrophy, and assessment of PR, RR, QRS, and QT intervals. Identification of any clinically significant findings and/or conduction abnormalities will be recorded on the CRF.

7.11.7 Intracranial Pressure Measurement

Intracranial pressure (ICP) measurement (cm of H₂O) will be assessed for all patients. The ICP measurement will be conducted by lumbar puncture and while the patient is under anesthesia.

Patients with a surgically implanted IDDD should undergo X-ray prior to lumbar puncture to verify the position of the catheter.

7.11.8 Brain Magnetic Resonance Imaging

Patients will undergo magnetic resonance imaging (MRI) of the brain. Brain structure volumes will be measured. Refer to the Study Operations Manual and/or MRI Manual for specific procedures and precautions.

7.11.9 Clinical and Other Laboratory Tests

Blood and urine samples will be collected as described in this section for clinical laboratory testing. All blood samples will be collected by venipuncture or via central line. The maximum volume of blood collected is presented by study visit in [Appendix 4](#).

Clinical laboratory tests will include the following (See [Table 7-2](#)):

Table 7-2 List of Laboratory Tests

Hematology:	Serum Chemistry:
- Hematocrit (Hct)	- Albumin (ALB)
- Hemoglobin (Hgb)	- Alkaline phosphatase (ALK-P)
- Mean corpuscular hemoglobin (MCH)	- Alanine aminotransferase (ALT; SGPT)
- Mean corpuscular hemoglobin concentration (MCHC)	- Aspartate aminotransferase (AST; SGOT)
- Mean corpuscular volume (MCV)	- Blood urea nitrogen (BUN)
- Platelet count	- Calcium (Ca)
- Red blood cell (RBC) count	- Carbon dioxide (CO ₂)
- White blood cell (WBC) count with differential	- Chloride (Cl)
	- Creatinine
	- Creatine phosphokinase
	- Gamma-glutamyl transferase (GGT)
	- Glucose
	- Lactate dehydrogenase (LDH)
	- Magnesium (Mg)
	- Phosphorus (P)
	- Potassium (K)
	- Sodium (Na)
	- Total and direct bilirubin
	- Total cholesterol
	- Total protein
	- Total thyroxine (T4)
	- Thyroid-stimulating hormone (TSH)
	- Triglycerides
Urinalysis:	
- Appearance (clarity and color)	
- Bilirubin	
- Blood	
- Glucose	
- Ketones	
- Leukocyte esterase	
- Microscopic examination of sediment	
- Nitrite	
- pH	
- Protein	
- Specific gravity	
- Urobilinogen	

Table 7-2 List of Laboratory Tests

Coagulation:	- Uric acid
- Prothrombin time (PT)	
- Partial thromboplastin time (PTT)	

Urine samples will be collected for determination of GAG concentration. Urine GAG will be analyzed and reported by a Sponsor-designated laboratory. Urine creatinine will be analyzed in the collected samples. Urine GAG concentration will be normalized to urine creatinine and reported as mg GAG/mmol creatinine.

7.11.10 Cerebrospinal Fluid Assessments

Cerebrospinal fluid samples will be collected via the IDDD or lumbar puncture and used to analyze standard safety laboratory parameters (chemistries, cell counts), albumin, GAG, and concentration of idursulfase enzyme. The CSF samples will also be analyzed for idursulfase-specific antibodies and antibodies with enzyme neutralizing activity (See Section 7.11.11).

Cerebrospinal fluid will be obtained from patients in the treated arm of the pivotal study and in the substudy at Screening (by lumbar puncture and under general anesthesia), during surgical implantation of the IDDD, prior to each intrathecal injection of investigational product, and at the EOS visit. Should the IDDD become clogged, undergo mechanical complications or otherwise not be accessible, the CSF sample may be obtained by lumbar puncture up to 12 times during the treatment phase of the study.

Patients in the no-treatment arm of the pivotal study will undergo lumbar puncture (under general anesthesia) to obtain CSF samples at the Screening and EOS Visits.

7.11.11 Antibody Assessments

Blood and CSF samples will be collected and evaluated by a Shire-designated laboratory for the presence of anti-idursulfase antibodies and antibodies with enzyme neutralizing activity.

7.11.12 Device Assessments

SOPH-A-PORT Mini S assessments will include measures of device implantation, device function, device longevity, and adverse events associated with the implant surgery or device. These data will be collected on the patient's CRF from the time of initial implantation.

As part of the assessment of the SOPH-A-PORT Mini S, it may be necessary to determine the levels of leachables from the device into the CSF and blood. Samples of stored CSF and serum may be used to determine the levels of leachable materials related to the IDDD.

7.11.13 Pregnancy Testing

Not applicable.

7.12 Sample Collection, Storage, and Shipping

Details for study procedures, including sample collection, are provided in the Study Operations Manual and/or Laboratory Manual for this study.

A variety of biological specimens will be collected from patients at the intervals indicated in the SOEs. These will be stored securely until analyzed. The patients' IDs will be kept confidential.

Samples will be stored until used up or for a maximum of 10 years after the last patient visit in this trial, after which any residual material will be destroyed.

7.13 Concomitant Medications, Therapies/Interventions, and Medical/Surgical Procedures Assessments

All medications, therapies/interventions administered to and medical/surgical procedures performed on patients from the time of informed consent through the follow-up contact are regarded as concomitant and will be documented on the CRF.

Non-permitted (per the exclusion criteria) medications, therapies, or surgical interventions will lead to exclusion from the study or a possible protocol violation depending on when the non-permitted event occurs.

7.14 Adverse Events Assessments

7.14.1 Definitions of Adverse Events and Serious Adverse Events

7.14.1.1 Adverse Events

An adverse event is any noxious, pathologic, or unintended change in anatomical, physiologic, or metabolic function as indicated by physical signs, symptoms, or laboratory changes occurring in any phase of a clinical study, whether or not considered investigational product-related. This includes an exacerbation of a pre-existing condition.

Adverse events include:

- Worsening (change in nature, severity, or frequency) of conditions present at the onset of the study
- Intercurrent illnesses
- Drug interactions
- Events related to or possibly related to concomitant medications
- Clinically significant abnormal laboratory values (includes shifts from baseline within the range of normal that the Investigator considers to be clinically important)
- Clinically significant abnormalities in physical and neurological examination, vital signs, ECG

Throughout the study, the Investigator must record all adverse events on the AE CRF, regardless of the severity or relationship to investigational product. The Investigator should treat patients with adverse events appropriately and observe them at suitable intervals until the events stabilize or resolve. Adverse events may be discovered through observation or examination of the patient, questioning of the patient or his parent(s)/legally authorized guardian(s), complaint by the patient or his parent(s)/legally authorized guardian(s), or by abnormal clinical laboratory values or physical findings.

In addition, adverse events may also include laboratory values that become significantly out of range. In the event of an out-of-range value, the laboratory test should be repeated until it returns to normal or can be explained and the patient's safety is not at risk.

Additional illnesses present at the time when informed consent is given are regarded as concomitant illnesses and will be documented on the appropriate pages of the CRF. Illnesses first occurring or detected during the study, and worsening of a concomitant illness during the study, are to be regarded as adverse events and must be documented as such in the CRF.

7.14.1.2 Elaprase-related Adverse Events

All patients will receive concomitant IV therapy with Elaprase throughout their participation in this study. Adverse events that are potentially related to IV Elaprase infusion will be captured. The most commonly reported adverse events that have been assessed as related to Elaprase in patients with Hunter syndrome are listed in Section 6.6.1. Note that, during weeks of IT dose administration, the IV infusion of Elaprase should be scheduled to occur a minimum of 48 hours after IT dosing in order to help distinguish adverse events related to IV compared to IT administration.

7.14.1.3 IDDD-related Adverse Events

Examples of adverse events related to use of the IDDD include, but are not limited to, the following: device failure (such as may occur with migration of the portal/catheter, occlusion of the portal/catheter, incorrect connection of IDDD components, fibrin sheath formation around the catheter tip), erosion of the portal/catheter through the skin, hematoma, implant rejection, or subcutaneous tract infection. A malfunction of the device (defined in Section 7.14.2.2) should not be entered as an adverse event unless this has physiopathological consequences such as those listed above. In the event of device failure (defined in Section 7.14.2.3), the device may need to

be replaced or repaired as needed. Hospitalization for such a procedure will be reported as a serious adverse event. Details of the cause of IDDD malfunction or failure will be recorded on the device Malfunction/Failure CRF. A list of the most common IDDD adverse events is included in [Appendix 4](#).

7.14.1.4 Device Surgical Procedure-related Adverse Events

Examples of adverse events related to device surgical procedures include, but are not limited to, the following: events that occur during or following IDDD implant/explant, IDDD adjustment, full revision, partial revision, IDDD removal, and delayed re-implantation after previous IDDD removal (such as complications of anesthesia, excessive bleeding, wound hematoma), and post-operative complications (such as post-operative infection).

7.14.1.5 Intrathecal Administration Process Adverse Events

Intrathecal administration process adverse events may include those caused by anesthesia during drug administration and other drug administration issues (eg, extravasation during infusion or hematoma due to the Huber needle), or complications of lumbar puncture.

7.14.1.6 Serious Adverse Events

A serious adverse event (SAE) is any adverse event occurring at any dose that results in any of the following outcomes:

- Death
- Is life-threatening
- Requires hospitalization (Note, however, for the purpose of this study, overnight hospitalizations post intrathecal administration of idursulfase-IT that are based on practical or logistical considerations, rather than safety will not result in a serious adverse event designation [See Section 7.6])
- Requires prolongation of existing hospitalization
- A persistent or significant disability or incapacity
- A congenital anomaly or birth defect

Important medical events that may not result in death, be life-threatening, or require hospitalization may be considered a serious adverse event when, based upon appropriate medical judgment, they may jeopardize the patient and may require medical or surgical intervention to prevent one of the outcomes listed in this definition. A life-threatening adverse event is defined as an adverse event that placed the patient, in the view of the initial reporter, at immediate risk of death from the adverse event as it occurred (ie, this definition does not include an adverse event that, had it occurred in a more severe form, might have caused death).

Hospitalization, which is the result of elective or previously scheduled surgery for pre-existing condition that has not worsened after initiation of treatment, should not result in a serious adverse event designation. For example, an admission for a previously scheduled ventral hernia repair would not be classified as a serious adverse event; however, complication(s) resulting

from a hospitalization for an elective or previously scheduled surgery that meet(s) serious criteria must be reported as serious adverse event(s). Furthermore, this does not apply to device failures resulting in scheduled surgical revisions, which should be reported as serious adverse events.

7.14.1.7 Unanticipated Adverse Device Effect

An unanticipated adverse device effect (UADE) is any serious adverse effect on health or safety or any life-threatening problem or death caused by, or associated with, a device, if that effect, problem, or death was not previously identified in nature, severity, or degree of incidence in the investigational plan or application (including a supplementary plan or application), or any other unanticipated serious problem associated with a device that relates to the rights, safety, or welfare of patients (21 Code of Federal Regulations [CFR] 812.3[s] or other regulatory requirements, as applicable).

7.14.2 Device-associated Definitions

7.14.2.1 Device Revision (Partial and Full)

Partial device revision: surgical revision/replacement of one or more component(s) of the device; other component(s) of the original device remain implanted and are not affected (eg, port revision).

Full device revision: the device is removed (explanted) in its entirety and a completely new device is implanted.

7.14.2.2 Device Malfunction

The device does not perform as intended, based on the description in the device's IFU, but does not require either a partial or full device revision.

7.14.2.3 Device Failure

The device irreversibly fails to perform as intended and requires either a partial or full device revision or removal.

7.14.3 Classification of Adverse Events and Serious Adverse Events

The severity of adverse events will be assessed by the Investigator based on the definitions shown in [Table 7-3](#). The severity of all adverse events and serious adverse events should be recorded on the appropriate CRF page as mild, moderate, or severe.

Table 7-3 Adverse Event Severity

Severity	Definition
Mild	No limitation of usual activities.
Moderate	Some limitation of usual activities.
Severe	Inability to carry out usual activities.

7.14.3.1 Clarification between Serious and Severe

The term “severe” is often used to describe the intensity (severity) of a specific event (as in mild, moderate, or severe myocardial infarction); the event itself, however, may be of relatively minor medical significance (such as severe headache). This is not the same as “serious,” which is based on the outcome or action criteria usually associated with events that may pose a threat to life or functioning (See Section 7.14.1.6). Seriousness (not severity) and causality serve as a guide for defining regulatory reporting obligations.

7.14.4 Relatedness of Adverse Events and Serious Adverse Events

The relationship of an adverse event or serious adverse event to study treatment (study drug, the IDDD, device surgical procedure, or IT administration process) will be assessed by the Investigator as follows. The relationship to study treatment will be categorized based on the definitions provided in Table 7-4.

- Relationship to idursulfase-IT
- Relationship to the IDDD (examples of IDDD-related adverse events are listed in Section 7.14.1.3)
- Relationship to a device surgical procedure (surgical implantation of the IDDD, partial or full device revision as described in Section 7.14.1.4)
- Relationship to the IT administration process (examples of IT administration process-related adverse events are listed in Section 7.14.1.5)

Table 7-4 Adverse Event Relatedness

Relationship to Treatment	Definition
Not Related	Unrelated to investigational product, device, device surgical procedure, or IT administration process.
Possibly Related	A clinical event or laboratory abnormality with a reasonable time sequence to administration of investigational product, device, device surgical procedure, or IT administration process, but which could also be explained by concurrent disease or other drugs or chemicals.
Probably Related	A clinical event or laboratory abnormality with a reasonable time sequence to administration of investigational product, device, device surgical procedure, or IT administration process unlikely to be attributable to concurrent disease or other drugs and chemicals and which follows a clinically reasonable response on de-challenge. The association of the clinical event or laboratory abnormality must also have some biologic plausibility, at least on theoretical grounds.
Definitely related	The event follows a reasonable temporal sequence from administration of the investigational product, device, device surgical procedure, or IT administration process, follows a known or suspected response pattern to the investigational product, is confirmed by improvement upon stopping the investigational product (de-challenge), and reappears upon repeated exposure (re-challenge). Note that this is not to be construed as requiring re-exposure of the patient to investigational product; however, the determination of definitely related can only be used when recurrence of event is observed.

The relationship of an adverse event or serious adverse event to IV Elaprase infusion will be assessed by the Investigator as described in Section 7.14.1.2.

7.14.5 Procedures for Recording and Reporting Adverse Events

7.14.5.1 Adverse Event Monitoring and Period of Observation

Adverse events will be monitored continuously throughout the study.

For the purposes of this study, the period of observation extends from the time at which informed consent is obtained until the patient's final evaluation of the study. For safety purposes, the final evaluation for patients who complete this study will be defined as the follow-up evaluation performed 7 (± 2) days after the EOS visit.

If the Investigator considers it necessary to report an adverse event in a study patient occurring after the end of the safety observation period, he or she should contact the Sponsor to determine how the adverse event should be documented and reported.

It is the responsibility of the Sponsor to ensure that each Investigator receives a copy of any CIOMS I/MDR report that has been submitted to the appropriate regulatory agencies notifying them of an unexpected drug-related serious adverse event or unanticipated adverse device effect (submitted by the Sponsor or manufacturer, respectively). The Investigator must ensure that the IRB/IEC receives a copy of the report and that a copy is also filed within their study files.

7.15 Pregnancy

Not applicable.

7.16 Abuse, Misuse, Overdose, and Medication Error

Abuse – Persistent or sporadic intentional intake of investigational product at a dose higher than prescribed per protocol (but below the dose defined for overdose) or when used for non-medical purpose (eg, altering one’s state of consciousness).

Misuse – Intentional or unintentional use of investigational product other than as directed or indicated at any dose, which is at or below the dose defined for overdose (Note: This includes a situation where the investigational product is not used as directed at the dose prescribed by the protocol).

Overdose – Intentional or unintentional intake of a dose of investigational product higher than the protocol-mandated dose. No clinical information on overdose is available. Idursulfase-IT has been well tolerated at the highest once monthly dose (30 mg) administered intrathecally to pediatric patients in clinical trials.

Medication Error – A mistake made in prescribing, dispensing, administration and/or use of the investigational product.

The Investigator must report abuse, misuse, overdose, and medication error to the Shire Pharmacovigilance and Risk Management Department AND to the Shire Medical Monitor on the SAE form. This form must be completed and FAXED or EMAILED within 24 hours of the Investigator's learning of the event (refer to the contact information for reporting of SAEs provided in Section 7.14.5.2).

7.17 Removal of Patients from the Trial or Investigational Product

A patient's participation in the study may be discontinued at the discretion of the Investigator. The following may be justifiable reasons for the Investigator to remove a patient from the study:

- The patient exhibits non-compliance with the study protocol that is considered disruptive to study conduct.
- The patient was erroneously included in the study.
- The patient develops an exclusion criterion.
- The patient suffers an intolerable adverse event.
- The study is terminated by the Sponsor.

The patient's parent(s) or legally authorized guardian(s) acting on behalf of the patient is free to withdraw consent and discontinue participation in the study at any time without prejudice to further treatment.

If the patient's parent(s) or legally authorized guardian(s) acting on behalf of the patient discontinues participation in the study, or the patient is discontinued by the Investigator, reasonable efforts will be made to follow the patient through the end of study assessments. The reason for refusal will be documented on the CRF. Any adverse events experienced up to the point of discontinuation must be documented on the AE CRF. If adverse events are present when the patient withdraws from the study, the patient will be re-evaluated within approximately 30 days of withdrawal. All ongoing serious adverse events at the time of withdrawal will be followed until resolution.

7.18 Other Study Procedures

7.18.1 Safety-related Study Stopping Rules

This study will be stopped and the safety data reviewed if any patient experiences a life-threatening serious adverse event or a death occurs, if either is considered possibly or probably related to the study treatment (investigational product, the IDDD, device surgical procedure, or

the IT administration process). After review of the safety data, the status of the study will be one of the following:

- Resumed unchanged
- Resumed with modifications to the protocol
- Terminated

Patient safety in this study will be monitored by an independent DMC until the last patient completes his last scheduled study visit/assessment. The DMC will be an external group overseeing the safety of the study treatment, including both the investigational product and the IDDD, and will operate according to a charter determining the scope of its activities and frequency of meetings (See Section 11.8 for additional details).

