1.3 Overview of Results of Phase I/II Studies

The safety and tolerability of ascending doses (1, 10, or 30 mg) of intrathecally administered idursulfase-IT were investigated in the first-in-human study HGT-HIT-045, a randomized, open-label, no-treatment controlled Phase I/II study in which idursulfase-IT was administered once monthly to pediatric MPS II patients via a surgically implanted IDDD (PORT-A-CATH[®] II Low Profile[™] Intrathecal Implantable Access System [PORT-A-CATH]) for 6 months in conjunction with once weekly IV infusion of Elaprase. Eligible patients who completed HGT-HIT-045 are receiving monthly IT injections of idursulfase-IT, in conjunction with Elaprase therapy, in extension study HGT-HIT-046. Across the HGT-HIT-045 and HGT-HIT-046 studies, long-term safety, pharmacokinetics (PK), and pharmacodynamics (PD) (effect on GAG concentration in CSF) have been evaluated. Effects of IT administration of idursulfase-IT on neurodevelopmental health have been evaluated using standardized tests of cognitive and adaptive functions.

Based on the data available from HGT-HIT-045 and HGT-HIT-046, idursulfase-IT has been found to be well tolerated at all doses administered without safety concerns related to the study drug. There have been no deaths or discontinuations due to adverse events (AEs) in either study, and no serious adverse events related to idursulfase-IT. The majority of serious adverse events in both studies have been associated with the PORT-A-CATH device, and designated as serious because of the requirement for overnight hospitalization for surgical revision/removal of the IDDD. The events related to the use of the IDDD included surgical removal and replacement of the device because of mechanical failures, primarily connector pin breaks and catheter slippage, to overnight admissions to the clinical site for a suspected device infection, and device removal because of wound issues.

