6.6.1 Infusion Reactions and Management

Infusions of proteins can be associated with reactions to the infusion that may or may not be immune mediated (hypersensitivity reactions). Thus, potential reactions to the infusion of an investigational product, including idursulfase-IT, are unpredictable. It is often difficult to clinically distinguish infusion reactions from hypersensitivity reactions. Symptoms may include headache, fever, sensory paresthesias (including feeling of warmth, tingling, or pain), rash, pruritus, or autonomic symptoms, such as dry mouth or gustatory abnormalities (including loss of smell and metallic taste). Changes in mental status or level of consciousness that are not caused by pre-medication may either occur acutely or develop post-injection over time.

The management of infusion reactions and hypersensitivity reactions is similar. The following steps may be taken, at the discretion of the Investigator, in the event of a suspected infusion related/hypersensitivity reaction and the management of such reactions should be based on the severity of the reaction:

- Treatment with medications such as antihistamines, antipyretics, and/or corticosteroids
- Stopping and resuming treatment
- Pretreatment with antihistamines and/or corticosteroids may prevent subsequent reactions in those cases where symptomatic treatment was required

Infusion-related reactions have been observed in patients receiving IV enzyme replacement therapy (ERT) with Elaprase, with symptoms including cutaneous reactions (rash, pruritus, and urticaria), pyrexia, headache, hypertension, and flushing. Previous experience with Elaprase is fully described in the Elaprase US Package Insert and the EU Summary of Product Characteristics (SmPC). Pretreatment with antihistamines and/or corticosteroids may prevent subsequent reactions in those cases where symptomatic treatment was required. The safety information reported from administration of Elaprase may be relevant to management of adverse events in relation to idursulfase-IT.

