10.7.1 Adverse Events

Adverse events will be recorded throughout the study and at early termination. Adverse events and medical conditions will be coded using the Medical Dictionary for Regulatory Activities (MedDRA) version 16.0 or later. Adverse events occurring on or after randomization and on or before the follow-up visit (scheduled 7 days after EOS Visit) will be summarized by treatment group, both overall and within system organ class (SOC) by preferred term. A summary of adverse events related to study drug will be presented. An adverse event will be considered related if indicated to be “possibly,” “probably,” or “definitely” related. A separate tabulation of IV Elaprase infusion-related adverse events will also be presented by treatment group. Adverse events will be tabulated by severity (mild, moderate, severe) and treatment group. In addition, those events which resulted in death or were otherwise classified as serious will be summarized and presented in a separate listing.

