11.8 Data Monitoring Committee

An independent, external DMC will be established to provide an ongoing, independent review and assessment of the safety data, and to safeguard the interests and safety of the participating patients in the study.

The DMC will be notified of all IDDD failures and IDDD-related complications at times defined in the DMC charter.

The DMC will consist of a biostatistician and two clinical experts. The DMC will adhere to a prospectively determined charter, which will be written by Shire or its designee and approved by the DMC. The charter will define the responsibilities of the DMC and Shire, describe the conduct of the meetings, and define the data sets to be reviewed. Serious adverse events and other data will be distributed to the members of the DMC periodically for review.

The first meeting of the DMC will be an orientation meeting and will be held prior to the start of the study. Thereafter, it is anticipated that the DMC will meet at least annually. The DMC will keep detailed minutes of their discussions during the meetings, which will be kept in strict confidence.

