11.11 Premature Closure of the Study

If the Sponsor, Investigator, DMC, or regulatory authorities discover conditions arising during the study which indicate that the clinical investigation should be halted due to an unacceptable patient risk, the study may be terminated after appropriate consultation between the Sponsor and the Investigator. In addition, a decision on the part of the Sponsor to suspend or discontinue development of the investigational product may be made at any time. Conditions that may warrant termination of the study or site include, but are not limited to:

- The discovery of an unexpected, significant, or unacceptable risk to the patients enrolled in the study
- Failure of the Investigator to comply with pertinent global regulations
- Submission of knowingly false information from the study site to the Sponsor or other pertinent regulatory authorities
- Insufficient adherence by the Investigator to protocol requirements

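### The mandatory study stop covers events rated possibly or probably related but leaves out definitely related, the highest rating on the protocol's own scale

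*Protocol*

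**What the plan says.** Section 7.18.1 of the Protocol sets a mandatory rule: "This study will be stopped and the safety data reviewed if any patient experiences a life-threatening serious adverse event or a death occurs". A causality condition is attached to both kinds of event, and it reads: "if either is considered possibly or probably related to the study treatment". Study treatment here covers the drug, the device, the device surgery and the intrathecal administration process. After the review the study may resume unchanged, resume with modifications, or be terminated.

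Section 7.14.4 has the investigator rate relatedness on Table 7-4, which has four levels: not related, possibly, probably and definitely related. The top level needs improvement when the product is stopped and reappearance on repeated exposure. The table adds that "the determination of definitely related can only be used when recurrence of event is observed".

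For the adverse event summaries, Section 10.7.1 says: "An adverse event will be considered related if indicated to be “possibly,” “probably,” or “definitely” related".

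**The concern.** The trigger names two of the three related levels and omits the strongest. An event whose causal link is supported by recurrence on re-exposure falls outside the automatic stop, while one rated only *possibly* related falls inside it. No safety reason supports that ordering.

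At stake is whether dosing of other children pauses automatically while the safety data are reviewed. If the rule is followed to the letter, a life-threatening recurrence rated *definitely* related leaves the pause to someone's discretion.

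**Working it through.** No power, alpha or event-rate figure bears on this point. The check sets the sections side by side.

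**1. Compare the levels.**

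| Source | Levels treated as related |
|---|---|
| Table 7-4 (Section 7.14.4) | possibly, probably, definitely |
| Section 10.7.1 | possibly, probably, definitely |
| Section 7.18.1, stopping rule | possibly, probably |

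The level left out is *definitely*. Neither Sections 7.18.1, 11.8 and 11.11 of the Protocol nor Section 8.3 of the SAP says that the trigger means at least possibly related, or that *probably* includes *definitely*.

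**2. Find which events can fall in the gap.** The event must be life-threatening or fatal, and it must be rated *definitely* related.

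- *First life-threatening event.* Without recurrence it cannot be rated *definitely*. If judged related, it is rated possibly or probably and the study stops. No gap.
- *Death.* It hardly fits a definition that requires improvement on de-challenge and return on re-challenge.
- *Purely device or surgical event.* The definition refers to stopping the investigational product, so it is hard to meet.
- *Recurrence after an episode that did not trigger the rule.* The earlier episode was not life-threatening, or was rated not related, and the reaction returns in life-threatening form at a later dose. Section 6.6.1 makes this reachable, because among the investigator's options for a suspected reaction it lists "Stopping and resuming treatment".
- *Recurrence after resumption.* The study was stopped, reviewed and resumed, and the event then returns.

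Only the last two cases remain.

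**3. Count the doses at which the rating could first become available.** Assume that all 32 planned treated pivotal patients receive all 12 injections:

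- Planned doses: 32 × 12 = 384.
- Second or later doses: 32 × 11 = 352.
- Share: 352 / 384 = 11 / 12 = 91.7%.

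This is a ceiling for the pivotal arm and not an event rate. The gap also needs an earlier episode of the same reaction in the same patient, with de-challenge, so the relevant number of doses is far smaller. Substudy patients, who are under the same rule, are not counted.

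**4. Look at the other safeguards.** Under Section 11.11, where an unacceptable risk emerges, "the study may be terminated after appropriate consultation between the Sponsor and the Investigator". Under Section 11.8, "Serious adverse events and other data will be distributed to the members of the DMC periodically for review", and the DMC is expected to meet at least once a year. The first is discretionary and the second periodic. No other automatic study-level stop appears in the text available. The serious adverse event reporting text of Section 7.14.5.2 and the DMC charter were not available to this review.

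**The case against.** The strongest reply is that the intent is obvious. Section 7.18.1 does not cite Table 7-4, and its phrase can be read as a threshold. Most criteria for *definitely* (plausible timing, improvement on de-challenge) also appear under *probably*, so an event that passes the stricter test would normally be considered at least probably related. An investigator could also rate the recurrence *probably*, or re-rate an earlier life-threatening episode as related, and either would stop the study.

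The safeguards also go beyond Sections 11.8 and 11.11. The Protocol has investigators receive reports of unexpected drug-related serious events and unanticipated device effects and pass them to the ethics committee. Section 11.2 requires prompt submission of safety reports, and Section 7.17 allows a patient to be removed for an intolerable adverse event. Finally, Section 1.3 reports "no serious adverse events related to idursulfase-IT" in the Phase I/II studies.

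Much of this stands. The intent is almost certainly at least possibly related, the likelihood is low, and the dose count says little about how often the gap would matter. It does not remove the point. Table 7-4 defines the levels separately, and Section 10.7.1 names all three when all three are meant. Re-rating is not required anywhere in the text available. None of the further safeguards is an automatic study-level stop. A mandatory safety rule should not depend on sites supplying an unwritten category.

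**Conclusion.** The concern holds. As written, the mandatory stop omits the strongest causality rating on the Protocol's own scale. The practical gap is small: it is confined to a reaction that escalates to life-threatening on re-exposure, or to a recurrence after the study has resumed, and few or no events may fall in it. The conclusion rests on a literal reading of Section 7.18.1 and on there being no wider trigger in the serious adverse event reporting text or the DMC charter. Even if such a trigger exists there, Section 7.18.1 would still be inconsistent with Table 7-4 and Section 10.7.1. It should be corrected because the consequence in a paediatric intrathecal trial could be serious and the correction is simple. It does not call the efficacy analysis into question.

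**What to change.** In Section 7.18.1, change the causality condition to *considered possibly, probably, or definitely related*, or equivalently *considered at least possibly related*. Check that the DMC charter and any serious adverse event reporting instructions use the same wording.

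The cost is one phrase in a protocol amendment. Section 11.10 requires ethics committee approval and submission to the authorities before a change is put into effect, so it can reasonably travel with the next amendment. Endpoints, sample size and statistical analysis do not change.
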